4.2 BASELINE

The Baseline (T0) visit will be performed for subjects who have met all eligibility criteria within 6 weeks of the Screening Visit, as soon as HIV-1 viral tropism, genotypic and/or phenotypic resistance results are available for review by Investigator. HIV RNA and TruCount Assay will be performed to ensure continued eligibility prior to the first Treatment Visit (T1). Subjects who have an HIV RNA result >400 copies/mL will be enrolled at the T1 visit. Subjects who have an HIV RNA result <400 copies/mL will be designated as screen failure.

The following assessments will be performed at the T0 visit:

- Change in concomitant medications (see [section 7.5](#))
- Collection of Blood Specimens (see [section 7.11](#)) for
 - Plasma HIV-1 RNA level
 - TruCount T Assay

4.3 TREATMENT PHASE

Treatment Phase begins with an evaluation of results of laboratory samples collected during the Screening Phase. Subjects who meet all eligibility criteria, as per data gathered from Screening Phase are to be treated. All subjects who fail to meet eligibility criteria will be considered screen failure and exit the study without further evaluation.

Eligible subjects will receive up to 25 treatments injections, given once per week (\pm 3 days) or until treatment failure, whichever occurs first. Eligible subjects will receive PRO 140 700mg administered as two subcutaneous injections within the first week of the Treatment Phase, followed by two subcutaneous injections of PRO 140 700mg, given once per week (\pm 3 days) for up to 24 weeks.

Treatment Phase is divided into two parts:

- Part 1: One-week treatment period [PRO 140 + failing ART]
- Part 2: 24-week treatment period [PRO 140 + OBT]

Note: A confirmatory HIV RNA test will be completed one week prior to initiation of treatment with PRO 140.

As shown in [Table 4-3](#), enrolled subjects will have IP along with failing ART for one week.

Table 4-3 Part 1: One week period [IP (PRO 140) + existing ART]

Study Drug	Dosage Form	IP concentration	Dosing Frequency and Amount	Route of Administration
PRO 140	Parenteral solution	175 mg/mL	2 injections of PRO 140 (2 X 2 mL/inj.) at T1 visit	SC injection

As shown in [Table 4-4](#), all enrolled subjects will receive PRO 140 along with optimized background therapy (OBT) for up to 24 weeks after completing the initial 7-day treatment period.

Table 4-4 Part 2: 24-week treatment maintenance period [PRO 140 + OBT]

Study Drug	Dosage Form	IP concentration	Dosing Frequency and Amount	Route of Administration
PRO 140	Parenteral solution	175 mg/mL	2 injections of PRO 140 (2 X 2 mL/inj.) per week for up to 24 weeks (T2 – T25)	SC injection

The study treatment (PRO 140 SC injections) will be administered by a qualified medical professional (MD, DO, PA, LPN, LVN, NP, RN, or CMA if permitted by state law) or self-administered by subjects depending on the study visit week.

Note: *Study treatment injections at T1, T2, T3, T7, T11, T15, T19 and T23 must be administered at clinic. The remaining study treatment injections may be self-administered by subjects outside the clinic.*

All study subjects will continue or adjust their current Optimized Background Therapy:

- At the end of 25-week Treatment Phase, or
- Anytime during the Treatment Phase, if treatment failure occurs or have met any other criteria for discontinuation of study treatment as specified in [section 5.2.1](#) of the protocol. Subjects

will be allowed to continue PRO 140 with existing OBT regimen while waiting for new regimen to be constructed by the Investigator.

Note:

- Subjects may return to clinic for an additional blood draw in-between the clinic visits for plasma HIV-1 RNA levels, per the discretion of the Investigator.
- Subjects who experience treatment failure at any time during the Treatment Phase will undergo the Treatment Failure (TF) Visit assessments and enter the Follow-up Phase of the study.
- Subjects who meet any criteria (other than treatment failure) for discontinuation of study treatment as specified in [section 5.2.1](#) of the protocol, will undergo End of Treatment Phase (EOT) Visit assessments and enter the Follow-up Phase of the study.
- Subjects who do not experience treatment failure will enter the Follow-up Phase of the study at the end of 25-week Treatment Phase.

Visits during the Treatment Phase will commence on T1, i.e. the date of first treatment, with weekly visits (\pm 3 days) thereafter. The first Treatment Visit (T1) will take place as soon as HIV-1 viral tropism, genotypic and/or phenotypic resistance results are available for review by Investigator, within 6 weeks of the Screening Visit.

4.3.1 Treatment Visit (T1) - Part 1 of Treatment Phase

The following assessments will be performed at the first treatment visit, unless otherwise specified:

Pre-Treatment

- Confirmation of eligibility criteria by reviewing test results and other criteria assessments performed at Screening Visit (see [section 7.2](#))
- Neurological assessment (see [section 7.9](#))
- Symptom-directed physical examination (see [section 7.7](#)),
- Change in concomitant medications (see [section 7.5](#))
- Any changes in medical history since Screening Visit (see [section 7.4](#)),
- Collection of Blood Specimens (see [section 7.11](#)) for

- Plasma HIV-1 RNA level
 - TruCount T Assay
 - PK sample for PRO 140
 - Anti-idiotypic antibodies to PRO 140
 - Serum concentration of ART drugs
 - HIV Drug Resistance Assay
- **Note:** *Blood sample for Plasma HIV-1RNA level, TruCount T Assay and HIV-1 Drug Resistance Assay will be collected at SV, T1, T2, T3, T7, T11, T15, T19, T23, EOT and TF visits.*
- **Note:** *PK sample for PRO 140 and Anti-idiotypic antibodies to PRO 140 will be performed at T1, T7, T15, EOT and TF visits*
- **Note:** *Serum concentration for ART will be performed at T1, T7, T15, visits, EOT and TF visits, as well as any Unscheduled Visit within the Treatment Phase as per discretion of the Investigator.*
- Urine Pregnancy Test (see [section 7.11.6](#))

Administration of study treatment [PRO 140]

Study treatment will be administered weekly as a subcutaneous injection in the abdomen.

Subjects will receive the study treatment delivered as two 1 mL injections on opposite sides of the abdomen.

Note: All study treatments (PRO 140) must be administered by a qualified medical professional (MD, DO, PA, LPN, LVN, NP, RN, or CMA if permitted by state law) or self-administered by subjects depending on the study visit week.

Post-Treatment

- Injection Site Reaction Assessment (see [section 7.13](#))

➤ **Note:** *To assess injection site reactions, the investigator will use the DAIDS AE grading table (refer to [section 16.3](#)).*
- Assessment of Adverse Events (AE) (see [section 9](#))
- Vital Signs (see [section 7.10](#)) will be assessed within 15 minutes of study treatment administration.

Note: Investigator should determine the Optimized background therapy (OBT) regimen based on genotypic and/or phenotypic results obtained during Screening Phase and provide the appropriate prescription to the study subject at Treatment Visit 1 (T1).

OBT is a standard-of-care regimen comprised of 3 or more antiretroviral agents selected by the investigator based on treatment history and genotypic and/or phenotypic assessments. The use of another experimental agent (e.g., ibalizumab) to create a viable HIV suppressive OBT regimen in certain subjects with severely limited approved and available therapeutic options will be allowed with the prior approval from sponsor.

4.3.2 Treatment Visit-2 (T2) to Treatment Visit-25 (T25) - Part 2 of Treatment Phase

The following assessments will be performed at each visit, unless otherwise specified:

- Assess for any Adverse Events and changes in Concomitant medications (see [section 9](#) and [7.5](#)),
- Symptom-directed physical examination (see [section 7.7](#)),
- Neurological Assessment (see [section 7.9](#))
 - **Note:** *Neurological assessment will be performed at T3, T7, T11, T15, T19, T23 visits*
- Vital Signs (see [section 7.10](#))
 - **Note:** *Post-treatment vital signs will be assessed within 15 minutes following study treatment administration when performed inside clinic.*
- Collection of Blood Specimens (see [section 7.11](#)) for
 - Plasma HIV-1 RNA level
 - TruCount T Assay
 - HIV-1 Drug Resistance Assay
 - PK sample for PRO 140
 - Serum concentration of ART drugs
 - Anti-idiotypic antibodies to PRO 140
 - **Note:** *Blood sample for Plasma HIV-1RNA level, TruCount T Assay, and HIV-1 Drug Resistance Assay will be performed at SV, T1, T2, T3, T7, T11, T15, T19, T23, EOT and TF visits*
 - **Note:** *PK sample for PRO 140 and Anti-idiotypic antibodies to PRO 140 will be performed at T1, T7, T15, EOT and TF visits*

- **Note:** Serum concentration for ART will be performed at T1, T7, T15, visits, EOT and TF visits, as well as any Unscheduled Visit within the Treatment Phase as per discretion of the investigator.
- Study Treatment Administration (PRO 140)
- Injection Site Reaction Assessment (see [section 7.13](#))
 - **Note:** To assess injection site reactions, the investigator will use the DAIDS AE grading table (refer to [section 16.3](#)).
- Subject-perceived Injection Site Pain Assessment (see [section 7.14](#))
 - **Note:** Subject-perceived injection site pain will be assessed using the Pain Visual Analog Scale (VAS) prior to study treatment administration assessing average pain at injection site since last treatment.

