As shown in Table 0-2, after 7 days all subjects will enter the 24-week treatment period. During this period, all subjects will receive PRO 140 SC injection and Optimized Background Therapy. Optimized Background Therapy (OBT) is a standard-of-care regimen comprised of 3 or more antiretroviral agents selected by the investigator based on treatment history and genotypic and/or phenotypic assessments.

Table 0-2: 24-week treatment period [PRO 140 + OBT]

Study Drug	Dosage Form	IP concentration	Dosing Frequency and Amount	Route of Administration
PRO 140	Parenteral solution	175 mg/mL	2 injections of PRO 140 (2 X 2 mL/inj.) per week for up to 24 weeks (T2 – T25)	SC injection

Study participants will be regularly monitored for viral load following initiation of PRO 140, and will cease weekly study treatment injections should they experience treatment failure.

Subjects who experience treatment failure at any point during the Treatment Phase will undergo the Treatment Failure (TF) Visit assessments and then return in 4 weeks (\pm allowed window) for the Safety Follow-up Visit.

Treatment failure is defined in terms of virologic non-response and virologic rebound in the Open-Label Treatment Phase of the study.

(1) *Virologic non-response is defined as two consecutive viral load results of:*

- $< 0.5 \log_{10}$ copies/mL decrease in HIV-1 RNA at Day 7 of Treatment Phase Part 2. [Assessment Timepoint: T3 and T4 visit]
- $< 1.0 \log_{10}$ copies/mL decrease in HIV-1 RNA at or after Week 4 of Treatment Phase Part 2 unless HIV-1 RNA < 400 copies/mL [Assessment Timepoint: from T6 up to T25 visit].
- *Confirmed plasma HIV-1 RNA levels ≥ 400 copies/mL at Week 25 of Treatment Phase Part 2. [Assessment Timepoint: T25 visit]*

(2) *Virologic rebound is defined as two consecutive viral load results of:*

- $\geq 1.0 \log_{10}$ copies/mL increase in plasma HIV-1 RNA above nadir level* in Treatment Phase Part 2 [Assessment Timepoint: from T3 up to T25 visit] or

**Note: This refers to "Nadir" level in the Treatment Phase which starts from T2 visit*

Name of Sponsor: CytoDyn, Inc.	
Name of Study Product: PRO 140 (Humanized monoclonal antibody to CCR5)	
Protocol Number: PRO 140_CD02_OpenLabel	Therapeutic Indication: Human Immunodeficiency Virus Type-1 (HIV-1) Infection

 • ≥ 400 copies/mL after suppression to < 50 copies/mL in Treatment Phase Part 2. [Assessment Timepoint: from T3 up to T25 visit] 	

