2 STUDY OBJECTIVES

The primary objective is to assess the efficacy, clinical safety and tolerability parameters of PRO 140 in reducing HIV-1 viral load in patients on their current ART (failing regimen) during the 1-week treatment period, and in combination with Optimized Background Therapy during the subsequent 24-week treatment period.

The primary efficacy endpoint is proportion of participants with ≥ 0.5 log10 reduction in HIV-1 RNA viral load from baseline at the end of the initial 1-week treatment period.

The secondary efficacy endpoints will be proportion of participants with ≥ 1 log10 reduction in HIV-1 RNA viral load from baseline at the end of the initial 1-week treatment period, mean change from Baseline in HIV-1 RNA levels (log10 copies/mL) at the end of the initial 1-week treatment period, percentage of participants achieving HIV-1 RNA < 400 copies/mL at week 25, percentage of participants achieving HIV-1 RNA < 50 copies/mL at week 25, mean change from Baseline in HIV-1 RNA levels (log10 copies/mL) at week 25, mean change from Baseline in CD4 cell count at the end of 1-week treatment period, and mean change from Baseline in CD4 cell count at week 25.

Safety assessments include evaluation of emergence of Dual/Mixed (D/M)- and CXCR4-tropic virus in patients who had exclusive CCR5-tropic virus at study entry, tolerability of repeated subcutaneous administration of PRO 140 as assessed by study participants (using Visual Analogue Scale) and by investigator—evaluation of injection site reactions, frequency of treatment-related adverse events resulting in study drug discontinuation, frequency of Grade 3 or 4 adverse events and frequency of treatment-emergent serious adverse events.

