4 STUDY SCHEDULE

As shown in [Figure 4-1](#), this study is divided into three phases: Screening, Treatment and Follow-up.

Figure 4-1: Study Schematic

(1) **Screening Phase:** This phase lasts up to 6 weeks, consists of Screening Visit (SV) and begins with signing of Informed Consent. Assessments performed during this phase determine the subject's final eligibility for study participation. First treatment will be administered within 42 days of Screening Visit.

All subjects will continue taking their existing ART (failed regimen) during the Screening Phase and first week of the Treatment Phase (Part 1).

(2) **Baseline:** The Baseline (T0) visit will take place within 6 weeks of the Screening Visit, as soon as HIV-1 viral tropism, genotypic and/or phenotypic resistance results are available for review by Investigator. HIV RNA and TruCount Assay will be performed to ensure continued eligibility prior to the first Treatment Visit (T1).

(3) **Treatment Phase:** Subjects will receive up to 25 treatments, given approximately every week (window period of ± 3 days) or until treatment failure is experienced, whichever comes first.

The first Treatment Visit (T1) will take place within one week of the T0 visit.

The injectable study treatment (PRO 140) will be administered by a qualified medical

professional (MD, DO, PA, LPN, LVN, NP, RN, or CMA if permitted by state law) or self-administered by subjects.

Note: *Study treatment injections at T1, T2, T3, T7, T11, T15, T19 and T23 must be administered at clinic. The remaining study treatment injections may be self-administered by subjects outside the clinic.*

Any time during Treatment Period Part 2, if treatment failure occurs, Investigator will readjust antiretroviral regimen based on HIV-1 genotypic and/or phenotypic drug resistance results obtained during the TF visit.

Subjects will be allowed to continue PRO 140 with existing OBT regimen while waiting for new regimen to be constructed by the Investigator.

Treatment failure is defined in terms of virologic non-response and virologic rebound in Part 2 of the Treatment Phase of the study:

a) Virologic non-response is defined as two consecutive viral load results of:

- $<0.5 \log_{10}$ copies/mL decrease in HIV-1 RNA at Day 7 of Treatment Period Part 2. *[Assessment Timepoint: T3 visit]*

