Physical Examination	X		X ^[4]		X ^[4]	X ^[4]		X	X												
Neurological Examination ^[5]			X			X		X		X		X		X		X		X		X	X
Vital Signs ^[6]	X			X	X	X		X		X		X		X		X		X		X	X
Body Mass Index	X																			X	X
ECG	X																				
Complete Blood Count ^[7]	X							X				X		X						X	X
Biochemistry ^[8]	X							X				X		X						X	X
Coagulation Indices ^[9]	X							X				X		X						X	X
Serum Pregnancy Test ^[10]	X																				
Urinalysis ^[11]	X							X				X		X						X	X
HBsAg	X																				
Plasma HIV-1 RNA level	X	X	X		X	X		X		X		X		X		X		X		X	X
TruCount T assay ^[12]	X	X	X		X	X		X		X		X		X		X		X		X	X
PK conc. to PRO 140 ^[13]			X					X				X		X					X	X	

Procedure/Assessments	Screening Visit	Treatment Phase (26 weeks)															In case of Treatment Failure		
		ART only (1 week)		IP + ART (1 week)		IP + OBT (24 weeks)													
Visit	SV	T0	T1		T2	T3	T4-6	T7	T8 - 10	T11	T12-14	T15	T16-18	T19	T20-22	T23	T24-25	EOT	TF
			(Pre-Rx)	(Post-Rx)															
Window Period		Within 6 weeks of the Screening visit	Within 1 week ±3 days since T0	1 week ±3 days since last treatment															
Serum conc. of ART Drugs ^[14]			X					X				X						X	X
Urine Pregnancy Test ^[10]			X																
Pre-enrollment Eligibility		X	X																
PRO 140 + Existing ART Regimen			X																
PRO 140 + OBT Administration				X	X	X	X	X	X	X	X	X	X	X	X	X	X		
Injection Site Reaction Assessment ^[15]				X	X	X	X	X	X	X	X	X	X	X	X	X	X	X	
Injection Site Pain Assessment (VAS) ^[16]				X	X	X	X	X	X	X	X	X	X	X	X	X	X	X	
HIV-1 Trofile® Assay ^[17]	X																		X
HIV-1 Drug Resistance Assay ^[18]	X		X		X	X		X		X		X		X		X			X
HIV-1 PhenoSense® Entry Assay ^[19]	X																		X
Anti-idiotypic antibodies to PRO 140			X					X				X						X	X
Blood sample collection for exploratory analysis ^[20]	X																		X
Adverse Events				X	X	X	X	X	X	X	X	X	X	X	X	X	X	X	
Concomitant Medications	X	X	X	X	X	X	X	X	X	X	X	X	X	X	X	X	X	X	

Foot Notes:

- [1] Informed consent must be obtained prior to patient participation in any protocol-related activities that are not part of routine care.
- [2] Initial evaluation of patient eligibility will be performed by Investigator.
- [3] Medical history, past surgeries, disease history, history of substance abuse, social history, blood transfusion history, and current therapies (medications and non-medication).
- [4] Symptom-directed physical examination

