7.11.7 Plasma HIV-1 RNA level and TruCount T Assay

- Frequency of testing: At SV, Treatment Visits 1, 2, 3, 7, 11, 15, 19 and 23, as well as EOT and TF visits. In addition, blood sample will also be collected at all Treatment Failure Follow-up (TF-FU) Visits or Non-Treatment Failure Follow-up (NTF-FU) Visits.
- To assess antiretroviral therapeutic response to PRO 140

Note: *Plasma HIV-1 RNA level will be measured using Human Immunodeficiency Virus 1 (HIV-1), Quantitative, RNA (Abbott RealTime) test.*

TruCount T Assay includes measurement of Absolute Lymphocytes, CD3 cell count, CD4 cell count, CD8 cell count, CD3%, CD4% and CD8%

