8.2 DESCRIPTION OF STUDY ENDPOINTS

8.2.1 Primary Endpoint

The primary endpoint for this study is proportion of participants with a $\geq 0.5 \log_{10}$ reduction in HIV-1 RNA viral load from baseline to the end of the initial 1-week treatment period.

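### Nothing requires the T2 viral load, on which the primary endpoint rests, to be drawn before the first OBT dose, so in this single-arm study up to 3 days of OBT could be credited to PRO 140

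*Protocol*

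**What the plan says.** **Endpoint and sample.** Section 2 sets the primary endpoint as a "reduction in HIV-1 RNA viral load from baseline at the end of the initial 1-week treatment period", with a threshold of 0.5 log10; Section 8.2.1 has "from baseline to the end of the initial 1-week treatment period". Section 7.11.7 schedules plasma HIV-1 RNA "At SV, Treatment Visits 1, 2, 3, 7, 11, 15, 19 and 23, as well as EOT and TF visits", so T2 is the only scheduled measurement at the end of Part 1.

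**Visit window.** Table 4-1 gives treatment visits from T2 a window of "1 week ±3 days since last treatment", and Section 4 says treatments are "given approximately every week (window period of ± 3 days"). T2 has no tighter window.

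**Start of OBT, by elapsed time.** The Synopsis says "after 7 days all subjects will enter the 24-week treatment period". Section 4.3 gives PRO 140 with OBT "after completing the initial 7-day treatment period". Section 1.6.1.1 places the change after one week. Sections 3 and 4 keep subjects on the failing regimen through the first week of treatment.

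**Start of OBT, by visit.** Tables 0-2 and 4-4 index Part 2 as T2 to T25. Table 4-1 puts T2 under the PRO 140 plus OBT heading. The nadir notes in Sections 4.3.4 and 5.2.1 date Part 2 from T2.

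**Prescription.** Section 4.3.1 has the investigator determine OBT and "provide the appropriate prescription to the study subject at Treatment Visit 1 (T1"). The subject can therefore hold the new regimen throughout Part 1.

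**The concern.** Part 1 exists to show what PRO 140 does when added to a regimen that is not working. Section 1.4.2.9 describes the same week in the parent trial as functional monotherapy, and that trial had a placebo arm. Here every subject receives PRO 140 (Section 8.1) and nobody is randomized (Section 8.4), so the whole T2 change is read as the PRO 140 response.

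OBT is a regimen of three or more antiretrovirals chosen from resistance results. If it begins before the T2 sample, its effect enters the primary endpoint and cannot be separated afterwards. The two ways of timing the switch agree only when T2 falls exactly 7 days after T1. When T2 is later but still within its window, the elapsed-time wording allows OBT first and the sample second.

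An analysis plan can exclude or reclassify such values, but it cannot recover an uncontaminated end-of-week measurement once OBT has been taken.

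**Working it through.** The protocol gives no power calculation or assumed response rate (Section 8.3 rests the sample size on clinical judgement), so there is no stated figure to reproduce. The check is window arithmetic plus a reading of the text.

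**Step 1: when T2 can fall.** Count T1 as day 0. The window is 7 − 3 = day 4 to 7 + 3 = day 10.

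**Step 2: possible OBT exposure before the sample.** Under the elapsed-time wording, OBT days before T2 = T2 day − 7, where positive.

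| T2 day | OBT days before sample, elapsed-time wording | OBT days before sample, if OBT begins at T2 after the draw |
|---|---|---|
| 4 to 7 | 0 | 0 |
| 8 | 1 | 0 |
| 9 | 2 | 0 |
| 10 | 3 | 0 |

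The maximum is 3 days, or 3/10 = 30% of the interval being judged.

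**Step 3: does any text rule this out?** At T1, Section 4.3.1 lists blood sampling under pre-treatment procedures, and Table 4-1 splits T1 into before and after treatment. Section 4.3.2, which covers T2, gives no such order for HIV-1 RNA relative to either OBT or the injection. Section 7.11.11 takes ART drug levels at T1, T7, T15, EOT and TF but not at T2, so no scheduled assay would show whether OBT had begun. Section 7.6 does record a start date for each medication.

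**Step 4: size per subject.** An OBT effect of 0.5/3 = 0.167 log10 per day would reach the threshold in 3 days without PRO 140; a smaller effect could carry a subject who was just short of it. One changed classification among 25 subjects moves the responder rate by 1/25 = 4 percentage points.

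**Step 5: illustration of scale.** Every input here is an assumption, because the protocol gives none. Let the PRO 140 fall at T2 be normal with mean m from 0.5 to 1.0 log10 and SD s of 0.4 or 0.6, and let 3 days of OBT add d = 0.3 or 0.6 log10 in a fraction f = 20% of subjects.

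- Responder probability without OBT: P0 = 1 − Φ((0.5 − m)/s)
- With OBT: P1 = 1 − Φ((0.5 − m − d)/s)
- Inflation of the overall rate: f × (P1 − P0)
- Smallest in this range (m = 1.0, s = 0.4, d = 0.3): 0.2 × (0.977 − 0.894) = 0.017, or 1.7 points
- Largest (m = 0.5, s = 0.4, d = 0.6): 0.2 × (0.933 − 0.500) = 0.087, or 8.7 points

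The result is proportional to f, which the documents do not allow anyone to estimate; if no subject takes OBT before the draw, it is zero.

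**The case against.** The strongest reply is that the protocol, read as a whole, starts OBT at T2 and treats 7 days as the nominal gap between visits. The Synopsis sentence and its counterpart in Section 4.3 both refer to tables indexed T2 to T25. The failure criteria put day 7 of Part 2 at T3 and week 4 at T6, which makes T2 day 0 of Part 2, and Sections 4.3.4 and 5.2.1 date Part 2 from T2. This is a reasonable reading and may well be what was intended. But it has to be inferred, and even then no sentence puts the blood draw ahead of the first OBT dose.

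A reader might infer three stronger points that the documents do not support:

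- **That the protocol gives three conflicting OBT start dates.** It does not. Handing over a prescription at T1 is not a start date, and Sections 3 and 4 keep the failing regimen going through Part 1. The T1 prescription matters only because it makes an early start possible.
- **That a T2 on day 4 makes the endpoint defective through short exposure.** The 3-day window is stated consistently, and analysis windows are a matter that Sections 8 and 8.6.2 leave to the SAP, which is not at hand.
- **That the responder rate is badly inflated.** Large figures appear only if every subject sits at the edge of the window, or if PRO 140 is assumed to do nothing. Those are extremes under assumed values, not an expected bias.

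It is also fair to say that OBT start dates are already collected under Section 7.6, and that the analysis is descriptive (Section 8.7.4.1) and meant to supplement other data (Section 8.3). Both limit the consequence, but neither keeps OBT out of the primary sample.

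**Conclusion.** The point holds in a limited form. The protocol times the move to OBT both by elapsed days and by the T2 visit, gives out the prescription a week ahead, and never requires the primary-endpoint sample to precede the first OBT dose. A fully compliant subject could have up to 3 days of OBT counted as PRO 140 response, in a study with no comparator.

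The 3-day maximum follows from the protocol's own window and needs no assumed effect. The 4 points per changed classification hold at 25 subjects; Section 8.3 leaves the final number open, and the figure is larger with fewer. The illustrated inflation of 1.7 to 8.7 points depends on an assumed 20% of subjects affected and on assumed effects and SDs. The direction, towards a higher responder rate, assumes only that OBT does not raise viral load. The frequency, and so the actual bias, is unknown. The change is worth making because it is cheap and must be in place before the sample is drawn.

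**What to change.** 1. Reconcile the passages on when OBT starts relative to T2: the Synopsis, Sections 1.6.1.1, 3, 4, 4.3, 4.3.1, 4.3.2, 4.3.4 and 5.2.1, and Tables 0-2, 4-1 and 4-4. Which rule applies is for the sponsor to decide; the passages need to say the same thing.
2. State in Sections 4.3.2 and 8.2.1 that the primary-endpoint HIV-1 RNA is the T2 sample drawn before the first OBT dose and before the T2 injection. Defining it as the last value before OBT would not help: for a subject who starts OBT before T2, the last scheduled value is the T1 pre-dose sample, and the change would be zero by construction.
3. Use the OBT start date already recorded under Section 7.6, adding the time of the first dose when it falls on the T2 day, to flag T2 samples drawn after OBT began.
4. Report the primary endpoint with flagged subjects counted as non-responders, and the as-observed result as a sensitivity analysis. If OBT can only lower viral load, the two results bracket the PRO 140 response in flagged subjects. With 25 subjects they differ by 4 points for each flagged subject who met the threshold.

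The cost is some protocol wording, one conditional eCRF field and one table. The downside is that a few subjects who attended within the permitted window may count as non-responders, which could lower the reported rate slightly; the as-observed result shows by how much.
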